Study Aims	 In fatigued adult outpatients with a primary brain tumour, and in the setting of a multi-centre randomised controlled trial: Assess the feasibility of delivering a structured lifestyle intervention (Health Coaching) and behavioural intervention (Patient Activation); Determine their acceptability to patients and manageability for professionals; Develop systems and pilot outcome measures for definitive RCTs of these interventions.
Primary Outcome	 The feasibility of delivering Health Coaching and Patient Activation to fatigued patients with a primary brain tumour. Feasibility will be assessed by meeting a priori defined standards for recruitment and retention as follows: recruitment will be feasible if 20 fatigued brain tumour patients can be recruited per centre over 12 months; retention will be feasible if total attrition at T2 (endpoint) is less than or equal to 40%.
Secondary Outcomes	 The acceptability of the interventions to patients. The manageability of the interventions for professionals. The development of systems and piloting outcome measures for future definitive RCTs of the interventions for fatigued brain tumour patients, including determination of mean change in outcome scale scores in each arm.
Study Design	Multi-centre, feasibility Randomised Controlled Trial with 16 weeks follow-up.
Patient Accrual	Eligible patients will be randomised to one of three study arms: con- trol (n=20); Health Coaching (n=20); Health Coaching plus Patient Activation intervention (n=20)
Analysis	Will be performed when all patients have completed their assess- ments at the end of the 16 week follow up and all data has been cleaned and database finalised.

1. INTRODUCTION

1.1 Background & Trial Rationale

Each year, more than 10,000 adults in the UK are diagnosed with a primary brain tumour.¹ Many or most of them experience fatigue, as evidenced by consistent reports of fatigue prevalence of between 40-70%.^{2,3} In turn up to forty percent⁴ of these fatigued brain tumour patients regard it as 'severe', which strongly and independently reduces multiple domains of quality of life.^{5,6} Fatigue is in other words, a problem both of high frequency and of high impact for people living with a brain tumour. The causes of fatigue are however multi-factorial and vary between individuals.⁷ As a result complex interventions such as structured lifestyle or behavioural interventions have been proposed as treatment for fatigue.⁸ These non drug-based treatments focus on changing aspects of the patient's lifestyle or behaviour. They have shown some efficacy in treating fatigue in patients with cancer arising out-with the central nervous system (CNS).^{9,10}

It is therefore plausible that structured lifestyle and behavioural interventions could be effective treatments for fatigue in patients with a brain tumour. However two problems with this hypothesis must be addressed. The first is that the conclusions of prior studies may not apply to patients with a brain tumour because these studies have largely recruited patients with cancer arising out-with the CNS. Brain tumours by contrast inhabit a privileged location and may directly alter cognition, physical function, personality, and/or seizure threshold. These relatively 'brain-tumour specific' co-morbidities could subvert strategies known to be effective in other cancer patient groups. The natural solution to this problem is to study how to treat fatigue in patients with brain tumours specifically.

The second problem is that most prior studies included patients with little or no fatigue at baseline. They cannot therefore directly answer the clinically relevant question, which is how best to treat individuals with clinically significant fatigue.⁸ Here the natural solution is to recruit and study patients with clinically significant fatigue. The few studies to do so suggest that complex interventions can be delivered effectively in fatigued patients.^{11,12} But specifically which structured lifestyle and behavioural interventions could be studied?

A structured lifestyle intervention: Health Coaching

Health Coaching is a lifestyle intervention which targets basic elements of diet, exercise, sleep and stress. It has been developed and delivered in the community for several years by our collaborator.¹³ Participants monitor their dietary intake, movement, rest and stress levels daily and in a structured way. Working in partnership with the Health Coach - an appropriately trained and qualified practitioner such as a personal trainer or physiotherapist - patients are supported to make incremental positive changes to their lifestyle. Because similar lifestyle interventions have been shown to be effective in treating fatigue in other cancer populations^{10,14}, we hypothesise that Health Coaching may be a effective treatment for fatigue in brain tumour patients.

A structured behavioural intervention: Patient Activation

Patient Activation (PA)¹⁵ is a behavioural intervention which leverages the individual's knowledge and confidence so that they are 'activated' to self-manage their condition. Importantly, PA captures not only the patient's *beliefs* about their ability to self-manage but also the *likelihood* that they will put these beliefs into action. Empowering patients through the framework of PA is thought to improve autonomy, quality of life, patient satisfaction, and cost-effectiveness.¹⁶ We hypothesise that Patient Activation could empower fatigued brain tumour patients to make and maintain lifestyle changes suggested by a Health Coach, potentially improving fatigue more than Health Coaching alone.

We wished to determine the level of existing evidence for these or similar lifestyle and behavioural interventions. To do this we systematically reviewed the evidence for effective interventions for fatigue in patients with a brain tumour.¹⁷ We found that nearly all eligible RCTs examined psychostimulant drug treatments, such as methylphenidate or modafinil ^{(e.g.)18-20} We found limited evidence that cognitive rehabilitation may improve mental fatigue as a secondary consequence of treating cognitive impairment.^{21,22} However, we found no high-quality studies of *any* non-pharmacological strategies such as lifestyle or behavioural interventions. Nearly all trials were further compromised by extending eligibility to non-fatigued patients. We concluded that there was a clear need for studies that evaluate

structured lifestyle and behavioural interventions for significant fatigue in people living with a brain tumour.

In this respect candidate studies would ideally meet some important criteria.

- They would ensure *clinical significance* by recruiting patients with high levels of fatigue at baseline.
- Given the limited state of current knowledge they would focus first and appropriately on studying the *feasibility* of delivering interventions in a Randomised Controlled Trial.
- They would show *novelty* by studying interventions previously unstudied in this population.
- They would *add value* by including a qualitative sub-study to understand the acceptability of interventions, alongside their feasibility.
- Credibility would be assured by the involvement of an accredited Clinical Trials Unit.
- The *exit strategy* would be clear: the feasibility study would develop systems in sufficient centres to recruit plausibly to a definitive trial.
- Such studies would ideally be run by a *collaborative and expert team* with a track record in neurooncology symptoms research.

1.2 Strategic importance of this research

The strategic vision of this study is to move towards better treatment for brain tumour-related fatigue. Nearly two-thirds of brain tumour patients experience fatigue, with 40% reporting that it has affected them severely.⁴ Fatigue is regarded as a 'top ten' clinical research priority in people with a brain or spinal cord tumour, by the UK James Lind Alliance (JLA) Priority Setting Partnership in Neuro-oncology.²³ More broadly by focusing on aspects of holistic assessment, lifestyle, late effects, and survivorship care, this study also reflects current thinking in the cancer field. Our approach aligns with the new Cancer Strategy in England, the Transforming Cancer After Treatment programme in Scotland, and the National Cancer Survivorship Initiative. This proposal directly targets a top priority of patients, charities, policymakers, and the wider research community.

2. TRIAL OBJECTIVES

2.1 Primary Outcome

The feasibility of delivering Health Coaching and Patient Activation to fatigued patients with a primary brain tumour.

Feasibility will be assessed by meeting a priori defined standards for recruitment and retention as follows:

- Recruitment will be feasible if 20 fatigued brain tumour patients can be recruited per centre over 12 months;
- Retention will be feasible if total attrition at T2 (endpoint) is less than or equal to 40%.

2.2 Secondary Outcome

- 1) The acceptability of the interventions to patients.
- 2) The manageability of the interventions for professionals.
- 3) The development of systems and piloting outcome measures for future definitive RCTs of the interventions for fatigued brain tumour patients, including determination of mean change in outcome scale scores in each arm.

2.3 Objectives and Key Deliverables

We will obtain ethical and centre-specific approval for the study; gain access to neuro-oncology adult outpatient clinics; recruit 60 fatigued brain tumour patients from three centres; appraise the feasibility of Health Coaching and Patient Activation in fatigued participants; pilot outcome measures of fatigue impairment, functional impact, and efficacy of self-management; pilot measures of the confounding variables of mood change and cognitive impairment; pilot health economic measures; and gain a deeper understanding of which components of the interventions are acceptable to whom and why, including their impact on the patient's primary carer. By doing so we will increase patient enrolment into early-phase clinical trials, while laying the ground for a definitive trial of non-pharmacological interventions for fatigue in people living with a brain tumour.

3. TRIAL DESIGN

3.1 General Design

BT-LIFE is a multi-centre feasibility Randomised Controlled Trial, summarised schematically here (Figure 1). It is designed in line with guidance on developing complex interventions from the MRC²⁴.

Figure 1: Schematic overview of the Brain Tumours, Lifestyle Intervention and Fatigue Evaluation (BT-LIFE) multi-centre feasibility Randomised Controlled Trial.

3.2 Inclusion Criteria

- 1. Patients aged 18 and above;
- 2. Diagnosed with any primary brain tumour;
- 3. >3 months post-completion of chemotherapy/radiotherapy;
- 4. Clinically and radiologically stable, as defined by no evidence of disease progression at most recent clinic appointment;
- 5. Moderate or severe fatigue (Brief Fatigue Inventory score ≥4/10, indicating at least 'moderate' severity of fatigue over the previous week) criterion for Randomisation.

3.3 Exclusion Criteria

- 1. Radiological or clinical concern at most recent appointment over disease progression;
- 2. Significant cognitive impairment, dysphasia, or visual impairment limiting ability to complete questionnaires;
- 3. Patients unable to give informed consent, or who are unable or unwilling to comply with interventions.

3.4 Recruitment/Setting

Patients will be recruited from neuro-oncology outpatient clinics in three tertiary centres: Edinburgh, Glasgow, and Manchester. Patients due to attend clinic and who meet inclusion criteria 1-3 above will be identified ahead of time. The Patient Information Sheet (PIS) will be posted to them together with a covering letter from their usual treating clinician. In this manner patients will have sufficient time to consider information about the study.

Edinburgh site: the information letter will also include a brief fatigue screening questionnaire (Brief Fatigue Inventory, BFI). In the covering letter patients will be asked to complete the screening questionnaire and take it with them to clinic if they are interested in taking part. In clinic, patients who have brought the completed questionnaire (and who have moderate-severe fatigue) will be asked by a member of their usual clinical team if they are interested in taking part in the study.

Glasgow and Manchester sites: During the clinic appointment a member of the usual clinical team will enquire whether the patient may be interested in taking part in the study. If so, the usual team member will themselves administer the screening Brief Fatigue Inventory.

Patients who score \geq 4/10 on the BFI will be eligible to continue in the full study. In all sites they will then be introduced to a Research Assistant or Research Nurse who will obtain informed consent from the patient

The Baseline Assessment (T0) will then be conducted. Follow-up Assessments (T1 and T2) will be arranged according to preference: either via further attendance at outpatient clinics, or by posting forms to participants to complete at home and return in a stamped addressed envelope.

Immediately after the Baseline Assessment, participants will be Randomised.

3.5 Randomisation Codes

After ensuring that the patient meets all the eligibility criteria and has consented to participate, the RA/RN will log onto www.sealedenvelope.com to randomise. An identification number will be issued which should be used in all correspondence. The RA/RN will notify SCTRU that a randomisation has occurred by emailing the randomisation confirmation securely to [contact]. Participants will be randomised to one of three study arms:

- Control (n=20);
- Health Coaching (n=20);
- Health Coaching plus Patient Activation intervention (n=20).

These group sizes reflect national guidelines on appropriate group sizes for a feasibility study.²⁵

Following randomisation, the participant's GP will be informed that they are taking part in the study.

It may be possible for participants to be recruited into other clinical trials, but this should be discussed with the CI, via SCTRU, before this is considered.

3.6 Withdrawal of Subjects

In recognition that fatigued participants may find Health Coaching tiring without wishing to withdraw from the study entirely, we will use a two-level framework for withdrawing consent.

Participants may partially withdraw consent at any point without having to give a reason (by withdrawing from active treatment in the study, for instance any participant who may find Health Coaching too onerous) and may continue to be followed up per protocol if they wish.

Participants may also fully withdraw consent at any point without having to give a reason. Data that has been gathered up to that point will be censored at the point of withdrawal, unless the participant wishes further that none of their data gathered at any time should be used, in which case it will be removed from study records.

Any participant who indicates to us that they wish to withdraw consent will be treated according to the "withdrawal of consent" flowchart (see supporting documents).

4. TREATMENT INTERVENTION

(Post-Randomisation):

Arm 1:

Control (n=20). Participants randomised to the control arm will continue to receive the highest possible standard of care and support from their neuro-oncology team, who will be informed that the patient has high fatigue. The participant will also receive high-quality written information on how to manage fatigue (see Fig 1 and supporting documents). They will then be followed up at T1 and T2.

Arm 2:

Health Coaching (n=20). Participants randomised to this arm will be treated as per Arm 1, but in addition will receive Health Coaching. They will be given an initial consultation form to complete. They will then receive a standardised first appointment with a trained Health Coach, in a clinical setting, by arrangement to suit. This initial face-to-face appointment will cover 1) consultation form review; 2) Measures (blood pressure, resting heart rate, height, weight); 3) Muscle Activation exercises 4) Review of guidance videos; 5) Goal setting until the next appointment. Participants will be given a fitbitstyle monitor to wear for the duration of the study.

Participants will then record standardised information about their lifestyle, on paper using a customdesigned diary form. The following information (the 'DREEMS' approach) will be gathered as often as possible (max daily) with assistance from the patient's carer/relative if desired:

Drink.	Caffeine, alcohol, water (number of each kind of drink per day, self-report)
Rest.	Total sleep (hours per day, self-report)
Eating.	Various food groups (portions per day, self-report)
Exercise	Aiming 3x30 minute sessions per week (self-report)
Movement.	Total number of steps taken per day (objective recording byfitbit-style monitor).
Stress.	Simple three-stage scale; low/neutral/high (self-report)

Health Coaching will be delivered for eight weeks. Over this period participants will receive a total of six sessions lasting 45 minutes each. Sessions will be delivered by telephone, Skype, Facetime, or in clinic, according to individual preference. At each treatment session the participant and Health Coach will review and set goals to incrementally change lifestyle areas according to need. This kind of semistructured but flexible approach is consistent with complex interventions shown previously to be efficacious for treating fatigue in cancer, such as exercise⁹, cognitive behaviour therapy¹¹, or yoga.¹² We will take steps to maximise parity of the intervention at all centres.

Arm 3:

Health Coaching plus Patient Activation intervention (n=20). Participants randomised to this arm will be treated as per Arm 2, but will also receive a Patient Activation (PA) intervention. In this intervention a trained PA coach will meet the participant and conduct a standardised semi-structured interview. These trained coaches will be supplied by *brainstrust*, a UK brain tumour charity with considerable experience in the field of personal coaching, and existing in-reach to all three study centres. *brainstrust* will ensure that all coaches delivering this intervention are trained to deliver it in a standardised way.

At the PA interviews participants will complete the Patient Activation Measure (PAM). The PAM is a 13-item measure²⁶, validated in patients with cancer,²⁷ that assesses Patient Activation. The focus of this short tool is to provide an initial measure of the participant's knowledge, skill and confidence for self-managing their fatigue. The coaching intervention will then incorporate and leverage this information using the theoretical underpinning of Dilts model of Logical Levels²⁸, which helps one understand one's health status and make choices about what to do. They will coach the participant to

appropriately leverage their activation to achieve their desired outcomes more effectively. Participants will be offered a second PA interview, identical in structure to the first, after a further four weeks.

Developing systems and piloting outcome measures: In line with MRC guidance²⁴ we will take the opportunity to develop and pilot systems and potential outcome measures for a future definitive trial. We will develop and use a structured clinical interview for fatigue, alongside the Brief Fatigue Inventory³² and the Functional Assessment of Chronic Illness Therapy-Fatigue (FACIT-F)³³, to study the impairment caused by fatigue over time. We will pilot the Psychological Outcome Profiles (PSYCHLOPS) tool³⁴ to track progress towards reducing the impact of fatigue on the most important functional outcomes for study participants.. As regards confounding variables, anxiety and depression will be screened using the Hospital Anxiety and Depression Scale³⁵ while cognitive function will be screened using the Addenbrooke's Cognitive Examination-III (ACE-III).³⁶ We will record prescribed medication at each study time-point. For all these outcomes we will gather pilot data on the magnitude of effect size in the treatment arms versus control, in order to estimate likely effect sizes in a larger trial.

We may in addition pilot instruments to examine the Health Economic costs and potential benefits of these interventions. We will assess health benefits using the EQ-5D which is the nationally-recommended instrument for this specific purpose.³⁷

4.2 Sampling time-points

T0 (baseline): Routine clinic-demographic information from notes review and GP contact, including past medical and psychiatric history, current medications and doses, and physical functional status. Battery of study materials as outlined. T1 (ten weeks post-randomisation): study materials as outlined. T2 (16 weeks post randomisation): study materials as outlined. In addition, qualitative interviews will be conducted on a subset of participants between 10 and 13 weeks post-randomisation (see Figure 1 and Figure 2 below).

Activity	SCREENING	T0 BASELINE	Wk 2- 10 INTERVENTION PHASE	T1 (Wk10) POST- INTERVENTION	T2 (Wk16) ENDPOINT
Brief Fatigue Inventory (BFI)	х			Х	х
Patient Written Informed consent	Х				
Eligibility Checklist		х			
Medical History		Х			
Demographics		Х			
Concomitant Medications		Х		Х	х
Semi-structured Clinical Interview for Fatigue (SCIF)		Х			
FACIT Fatigue Scale		Х		Х	х
PSYCHLOPS Pre-therapy		Х			
PSYCHLOPS Post-therapy				Х	Х
EQ-5D		Х		Х	Х
HADS		Х		Х	Х
ACE-III		Х		Х	х
Randomisation		Х			
Health Coaching Initial Consultation form ¹			Х		
Health Coaching appoint- ments ^{1,2}			Х		
Health Coaching Activity Log ^{1, 3}			Х		
Patient Activation interview			Х		
Qualitative interview ^{1, 5}			Х		

Figure 2: Treatment and Examination Schedule

- 1. For patient randomised to Arm 2 or 3 only.
- 2. Health Coaching will be delivered for eight weeks. Over this period participants will receive a total of six sessions lasting 45 minutes each, by telephone, Skype, or in person (clinic).
- 3. Participants will record standardised information as often as possible, up to a maximum of each day.
- 4. For patients randomised to Arm 3 only. PA coach will meet the participant and conduct a standardised semi-structured interview. Participants will be offered a second PA interview, identical in structure to the first, after a further four weeks.
- 5. Will be conducted in a sub-study of 24 participants within 3 weeks of T1.

4.3 Study materials

All participants will complete (at T0, T1 and T2) the measures outlined under '4.1: Develop systems and pilot outcome measures' above. Those receiving Health Coaching will also record data as outlined in the DREEMS model above. Professionals on the study will gather procedural data on recruitment, retention, the technical delivery of Health Coaching, and service use by participants.

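### Section 4.3 requires the BFI at T0 but Figure 2 does not schedule it, so within-arm BFI change may start from the eligibility score; the SCIF row has a similar clash

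*Protocol*

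**What the plan says.** - Section 4.3: "All participants will complete (at T0, T1 and T2) the measures outlined under" the part of Section 4.1 on developing systems and piloting outcome measures.
- Section 4.1 lists those measures. A structured clinical interview for fatigue (the SCIF) is to be used "alongside the Brief Fatigue Inventory" and FACIT-F to follow fatigue impairment over time. It adds: "For all these outcomes we will gather pilot data on the magnitude of effect size in the treatment arms versus control".
- The text of Section 4.2 gives for T0: "Battery of study materials as outlined". This agrees with Section 4.3.
- Figure 2, in the same section, has separate columns for screening and T0. The row beginning "Brief Fatigue Inventory (BFI" is marked at screening, T1 and T2, and its T0 cell is empty. FACIT-F, EQ-5D, HADS and ACE-III are marked at T0, T1 and T2. The SCIF is marked at T0 only.
- Section 3.2 makes the BFI an entry criterion: "Moderate or severe fatigue (Brief Fatigue Inventory score ≥4/10".
- Section 3.4 describes how the screening BFI is obtained. In Edinburgh the form is posted, and "patients will be asked to complete the screening questionnaire and take it with them to clinic if they are interested in taking part". In Glasgow and Manchester, at the clinic appointment, "the usual team member will themselves administer the screening Brief Fatigue Inventory". Consent, T0 and randomisation follow in that order. T1 and T2 are done in clinic or by post, as the participant prefers.
- Section 7.4 reports, for each arm, the mean change in outcome scale scores from baseline to week 16 with a 95% confidence interval.

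**The concern.** A site that works from Figure 2 collects no BFI at T0, and a site that works from Section 4.3 does. An analysis plan written later cannot recover a questionnaire that was never given.

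Under Figure 2, BFI change from baseline can start only from the eligibility score. Two things follow.

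1. **Selection.** Everyone enrolled scored at least 4 on that occasion, so some were having a worse week than usual. Their next score is expected to be lower without any treatment. Section 7.4 reports change within each arm, and that summary does not remove this fall.
2. **Collection.** In Edinburgh the score comes from a form completed at home, at an unstated interval before the visit. In the other two sites it is obtained at the appointment. The BFI refers to the previous week, so an Edinburgh score may describe a different week from the rest of that patient's baseline. The mode of completion may differ as well.

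At stake is how far the BFI pilot data can be read as change in fatigue when a definitive trial is planned.

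**Working it through.** **Step 1: set the schedule side by side.**

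| Measure | Section 4.3 with 4.1 | Figure 2 |
|---|---|---|
| BFI | T0, T1, T2 | Screening, T1, T2 |
| SCIF | T0, T1, T2 | T0 |
| FACIT-F, HADS, ACE-III, EQ-5D | T0, T1, T2 | T0, T1, T2 |

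The BFI and SCIF rows conflict with the text; the other four do not. Figure 1 is not shown, so it could not be checked for a T0 BFI.

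**Step 2: the plan's own figures.** The protocol gives no BFI mean, SD or retest correlation, so there is no BFI figure to reproduce. Its one calculated sample size, 49 per arm in Section 7.3, uses FACIT-F (difference 8, SD 12, alpha 0.05 taken as two-sided, power 90%). It reproduces: 48 by the normal approximation, and 48.26, rounded up to 49, by the t-test. Nothing below changes it.

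**Step 3: expected fall with no true change.** For a normal score cut from below,

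fall = (1 − r) × SD × φ(z) / p,

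where p is the share scoring 4 or more, z is the standard normal point with upper-tail area p, φ is the normal density, and r is the correlation between the screening and later scores. All inputs are assumptions: SD 2 to 2.5, r 0.5 to 0.8, and p 40% to 70%. The range for p is borrowed from the fatigue prevalence cited in Section 1.1, which is not the share of these clinics' patients scoring 4 or more on the BFI.

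- p = 0.70, SD 2, r = 0.8: φ(z)/p = 0.497, so fall = 0.2 × 2 × 0.497 = 0.20.
- p = 0.55, SD 2.5, r = 0.7: φ(z)/p = 0.720, so fall = 0.3 × 2.5 × 0.720 = 0.54.
- p = 0.40, SD 2.5, r = 0.5: φ(z)/p = 0.966, so fall = 0.5 × 2.5 × 0.966 = 1.21.

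A second set of assumptions starts from a clinic mean of 3 to 5 instead of p, with SD 2 to 2.5 and r 0.5 to 0.9. It gives 0.1 to 1.3. At SD 2.5 and r 0.7 it gives 0.42 (mean 5), 0.60 (mean 4) and 0.80 (mean 3).

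**Step 4: compare with the precision of the estimate.** At SD 2.5, r 0.7 and clinic mean 4, the simulated SD of change among those selected is 1.84.

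- 20 per arm: half-width of the 95% interval = 2.093 × 1.84 / √20 = 0.86.
- 12 per arm (40% attrition spread evenly, 20 × 0.60): 2.201 × 1.84 / √12 = 1.17.

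A spurious fall of 0.4 to 0.8 is thus roughly half to nearly all of the half-width at full retention.

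**Step 5: the between-arm difference.** In the same simulation, change from the screening score differed between two randomised arms by 0.006 points or less, which is simulation error. Selection happens before randomisation and acts alike on all arms.

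**Step 6: what a T0 BFI would achieve.** The fall that remains when change is measured from T0 depends on how strongly the T0 occasion error is correlated with the screening occasion error (SD 2.5, r 0.7, clinic mean 4; fall from screening 0.60):

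| Correlation of occasion errors | Fall measured from T0 |
|---|---|
| 0 | 0.00 |
| 0.5 | 0.30 |
| 0.9 | 0.54 |

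A repeat on the same day, covering nearly the same week, would lie towards the lower rows.

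**The case against.** The strongest reply is that this is a one-cell conflict with little consequence. Regression to the mean comes from enrolling on a BFI threshold, not from the empty cell, and a same-day repeat would leave much of it in place. In Glasgow and Manchester the screening BFI is given at the clinic appointment with consent and T0 to follow, so it is close to a baseline already. Administering the form may mean no more than handing it over, so a difference in mode is partly inference. Follow-up mode varies for every measure. The conflict could also be closed without another questionnaire, by letting Section 4.3 defer to Figure 2 and naming the screening score as the BFI baseline.

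Most of this stands, and it limits the point without removing it. The passages still disagree. Edinburgh still has a baseline taken at an unstated earlier time. Naming the screening score as baseline would make the text consistent but would keep both the full selection effect and the site difference.

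Three stronger readings should be resisted.

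- A reader might infer that the estimated treatment effect on the BFI is inflated. Section 4.1 asks for effect sizes against control, and that contrast is unbiased in expectation.
- A reader might infer that every site collects the score differently. Section 3.4 gives two procedures for three sites.
- A reader might infer that the candidate primary outcome of the definitive trial lacks a baseline. FACIT-F is scheduled at T0.

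**Conclusion.** The contradiction is real: Sections 4.1, 4.2 (text) and 4.3 put the BFI at T0, and Figure 2 does not. Section 4.3 also disagrees with Figure 2 on the SCIF.

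If Figure 2 governs, within-arm BFI change mixes any true change with regression to the mean, and it carries a difference between Edinburgh and the other two sites in the timing, and possibly the mode, of the starting score. The illustrative fall of 0.2 to 1.2 points rests on an assumed SD, retest correlation and share scoring 4 or more, and on a normal model for a bounded 0 to 10 scale. It shows that the effect could be comparable with the precision of the reported mean change; it is not an estimate for this trial.

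The consequence is confined to the descriptive within-arm change of one piloted measure. The scheduling gap does not affect the recruitment and retention criteria in Section 2.1, or FACIT-F. The issue is minor to moderate, and worth correcting because a missed T0 form cannot be collected afterwards.

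**What to change.** - Mark the BFI in the T0 column of Figure 2, completed the same way in all three sites and before randomisation.
- State in Section 7.4 that BFI change is measured from T0. Keep the screening BFI for eligibility only, and record its date.
- Report the BFI mainly as the between-arm difference adjusted for the T0 score, and say that within-arm change is not to be read as improvement. This is needed even with a T0 form, because a same-day repeat removes only part of the regression to the mean.
- Reconcile Section 4.3 with Figure 2 for the SCIF: either schedule it at T1 and T2, or exempt it from the general sentence.

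Cost: one short questionnaire per participant, one cell in Figure 2 and a few sentences of text. If the SCIF is scheduled at T1 and T2 rather than exempted, those interviews are an added cost. No sample size changes.
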